2.3 Overview of BCL-2 and venetoclax in AML

2.3.1 Venetoclax

See the Venetoclax Investigator's Brochure (IB) (Appendix) for additional details on nonclinical and clinical studies.

Bcl-2 overexpression has been implicated in maintaining the survival of AML cells and has been associated with resistance to chemotherapy and inferior overall survival (39). Venetoclax (VEN) is a potent and selective small-molecule inhibitor of Bcl-2 that has demonstrated cell-killing activity against a variety of leukemia cell lines, primary patient samples and leukemia stem/progenitor cells (40, 41). VEN also has been found to synergize with agents known to down-regulate Mcl-1, including azacytidine. (42)

Based on the mechanism of action and nonclinical and clinical data available to date, the safety profile of venetoclax is well described. The most common adverse drug reactions across all indications are nausea, diarrhea, hematological effects, and serious and/or opportunistic infections. Hematologic effects include neutropenia/febrile neutropenia, thrombocytopenia, anemia, and lymphopenia. Upper respiratory tract infections are among the most common infections. TLS is an important identified risk and is predominantly seen in the CLL population with high tumor burden. Based on pre-clinical data, decreased spermatogenesis has been identified as a potential risk for venetoclax.

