5.2 Dose Adjustments

5.2.1 Venetoclax and quizartinib dose adjustments for drug-related hematological adverse events (AEs) (all dose adjustments to follow guidelines in section 5.2.2)

Dose reduction/interruption/discontinuation decisions should be based on the CTCAE version 5.0 of the toxicity and the guidelines provided below.

- Patients with acute leukemias usually present with abnormal peripheral blood counts at the time therapy is started and myelosuppression is an expected event during the course of therapy for acute leukemias. Thus, no dose adjustments or treatment interruptions for myelosuppression will be planned for the first 4 cycles and/or in the presence of residual leukemia. After that, treatment interruptions and dose adjustments may be considered according to the following guidelines only when there is no evidence of residual leukemia.
 - Patients with a response (no marrow evidence of leukemia) and pre-cycle counts of neutrophils $>1.0 \times 10^9/L$ and platelets $>50 \times 10^9/L$ who have sustained low counts of neutrophils $<0.5 \times 10^9/L$ or a platelet count $<20 \times 10^9/L$ for more than 2 consecutive weeks in the current cycle, are recommended to have the treatment with

venetoclax and/or quizartinib interrupted or dose-reduced by one dose level after discussing with the PI until neutrophils recover to $\geq 0.5 \times 10^9/L$ and platelets to $\geq 20 \times 10^9/L$. If prolonged myelosuppression defined as ANC $< 0.5 \times 10^9/L$ and platelets $< 20 \times 10^9/L$ (more than 8 weeks) with evidence of a hypocellular marrow (marrow cellularity less than 5% without evidence of leukemia) is observed in these patients, both venetoclax and quizartinib will be discontinued. Delays in start of subsequent cycles greater than 8 weeks will be acceptable only for patients who are deriving clinical benefit and after discussion with the principal investigator of potential risk/benefit ratio and complete documentation of the degree of clinical benefit and reason for continuation on this regimen.

- If there are persistent peripheral blood blasts, or the bone marrow shows $>5\%$ blasts or evidence of leukemia by other assays, treatment may be continued regardless of neutrophil and platelet count with supportive care as needed. Dose-interruptions of venetoclax and/or quizartinib in these patients should be considered on an individual case and discussed with the PI and the sponsor.

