7.2 Evaluation During Treatment

- 7.2.1 During Cycle 1 Day 7-12 patients will be admitted to the inpatient service and have labs done at least daily to monitor closely for TLS, proliferative disease, and electrolyte changes. Patient can be treated as an outpatient if WBC $< 10,000$ with approval from the PI.

- 7.2.2 Physical exam on day 1 of each cycle (± 1 days) for the first 4 cycles.
- 7.2.3 CBC, platelet count, hemoglobin, differential at least twice weekly for the first 3 cycles, then at least once a week (differential can be omitted if WBC is $\leq 0.5 \times 10^9/L$). Outside labs may be used, but the PI/Treating physician must review all protocol specific outside lab results and determine the clinical significance of abnormal values then sign/date the results or dictate this process in the medical record.
- 7.2.4 Creatinine, total bilirubin, ALT, K, Mg, Ca, sodium, chloride, and CO₂ (HCO₃) on day 1 prior to start of quizartinib, at least twice weekly for the first 3 cycles, then at least once a week. For initial labs and initial management of electrolyte imbalances and prevention of tumor lysis syndrome patients will be admitted and monitored inpatient for cycle 1 Days 7-12 (section 5.5.4).
- 7.2.5 Laboratory tests can be ordered more frequently if mandated by development of peripheral blast/blood counts or electrolyte/liver function test abnormalities.
- 7.2.6 Bone marrow aspiration for differential and PCR for FLT3 on day 28 (± 7 days) of cycle 1, day 28 of cycle 3 (± 7 days), then every 2 cycles. Bone marrow tests can be ordered more frequently if mandated by development of peripheral blood counts. No repeat bone marrow is necessary if nonresponse or progressive disease can be unequivocally diagnosed from peripheral blood tests or, in patients with a WBC < 0.3 if the bone marrow test is considered noncontributory by the investigator at any time point.
- 7.2.7 Concomitant medication data will not be collected or entered into the case report form (Prometheus is the case report form for this study). Concomitant medication data will not be collected or entered into the case report form except for concomitant hydroxyurea if administered during the first cycle; however, the subject's medication record will contain a list of concomitant medications.

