10.0 ADVERSE EVENT REPORTING

10.1 Adverse event is any untoward medical occurrence that may present during treatment with a pharmaceutical product but which does not necessarily have a causal relationship with this treatment.

Adverse drug reaction is a response to a drug which is noxious and unintended and which occurs at doses normally used in man for prophylaxis, diagnosis, or therapy of disease or for the modification of physiologic function.

Assessing causal connections between agents and disease is fundamental to the understanding of adverse drug reactions. In general, a drug may be considered a contributory cause of an adverse event if, had the drug not been administered, 1) the event would not have happened at all, 2) the event would have occurred later than it actually did, or 3) the event would have been less severe.

The Investigator or physician designee is responsible for providing source documentation and assigning attribution for all AEs.

10.2 Adverse Events (AEs) will be evaluated against the most current version of the venetoclax and quizartinib IBs for expectedness. Adverse Events (AEs) will be evaluated according to the latest CTCAE version 5.0 and documented in medical record. AEs will be recorded in the Case Report Form (CRF). The Leukemia-specific Adverse Event Recording and Reporting Guidelines (Appendix G) will be used for reporting.

10.3 **Abnormal hematologic values will not be recorded on the case report form. For abnormal chemical values, the apogee or nadir (whichever is appropriate) will be reported per course on the case report form, unless the event is considered a DLT as listed in section 3.4.**

10.4 **Serious Adverse Event Reporting (SAE)**

An adverse event (AE) or suspected adverse event is considered “serious” if, in the view of either the investigator or the sponsor, it results in any of the following outcomes:

- Death
- A life-threatening adverse drug experience – any adverse experience that places the patient, in the view of the initial reporter, at immediate risk of death from the adverse experience as it occurred. It does not include an adverse experience that might have caused death if it had occurred in a more severe form.

- Inpatient hospitalization or prolongation of existing hospitalization, not to include planned hospitalization for ramp-up portion of the therapy
- A persistent or significant incapacity or substantial disruption of the ability to conduct normal life functions.

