11.3 Statistical Analysis Plan

All patients who receive any dose of the study agent will be included in the analysis for efficacy and safety. We will follow standard reporting guidelines for adverse events, and summarize safety data by category, severity and frequency. For the primary efficacy analysis, we will estimate the CRc rate for the combination treatment, along with the 95% credible interval. Patients who drop out of the study before completing all the cycles will be treated as “failures” for the primary analysis.

Patients’ demographic and clinical characteristics will be summarized using descriptive statistics. Specifically, categorical covariates will be summarized by frequencies and percentages and their associations with responses will be assessed using Fisher’s exact test or its generalization. Continuous covariates will be summarized by means, standard deviations, medians and ranges, and the difference between responses groups will be assessed using the Wilcoxon rank sum test. Paired t-tests or Wilcoxon signed-rank tests will be used to determine the immunological and molecular changes in the peripheral blood and bone marrow from baseline to the time of response, and to the time of disease progression.

We will estimate the rates of partial response and bone marrow blast reduction $\geq 50\%$ within 3 months, along with 95% confidence intervals. For each subject, duration of response (DOR), event-free survival time and overall survival time will be calculated. DOR is defined as the time period from the first documentation of CRc to disease

recurrence, disease progression, or death whichever occurs first. Event-free survival time is defined as the time period from the date of treatment initiation to the date of documented treatment failure, relapses from CRc, or death from any cause, whichever occurs first. The observed DOR/EFS will be censored at the last follow-up if the patient is alive and no events observed. The overall survival time is defined as the time duration from treatment start till death or last follow-up if the patient is alive. The distributions of time-to-event endpoints including OS and DOR will be estimated using the Kaplan-Meier method. Comparisons of time-to-event endpoints by important covariate subgroups will be made using the log-rank tests. Progressive disease will be determined using ELN (2017) recommendations and is defined as any one or more of the following:

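### Section 10.3 keeps blood-count values off the case report form, so the grade, nadir and duration of cytopenia in patients with a leukemia-free marrow cannot be tabulated by dose level

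*Combined protocol and SAP*

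**What the plan says.** - **CRF rule.** Section 10.3: "Abnormal hematologic values will not be recorded on the case report form". The next sentence asks for the highest or lowest abnormal chemistry value per course, "unless the event is considered a DLT as listed in section 3.4". By its grammar that exception belongs to chemistry; whether it also covers hematology is not stated.
- **Adverse events.** Section 10.2 sends CTCAE v5.0 adverse events to the CRF without excluding hematologic ones, and adds: "The Leukemia-specific Adverse Event Recording and Reporting Guidelines (Appendix G) will be used for reporting". Section 10.4 requires SAEs to be reported and gives blood dyscrasias as an example.
- **Safety analysis.** Section 11.3 says it will "summarize safety data by category, severity and frequency". Safety and tolerability is a phase II secondary objective (section 1.2).
- **Counts drawn.** Section 7.2.3: "CBC, platelet count, hemoglobin, differential at least twice weekly for the first 3 cycles, then at least once a week".
- **Known effects.** Section 2.3.1 on venetoclax: "Hematologic effects include neutropenia/febrile neutropenia, thrombocytopenia, anemia, and lymphopenia". Section 2.2 names bone marrow as a principal target organ of quizartinib in animals.
- **Use of counts in treatment.** Section 5.2.1 bases interruption, reduction and discontinuation on counts in certain responders "who have sustained low counts of neutrophils" or platelets below set thresholds.
- **RP2D.** Sections 3.3, 3.5 and 11.1 base the choice on efficacy, safety and pharmacodynamic data. The RP2D may be below the MTD.

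**The concern.** While leukemia is present, low counts mix disease with drug effect, and leaving them ungraded is defensible. Once the marrow is clear that reason weakens, and section 5.2.1 itself acts on counts in some of these patients under a heading about drug-related hematological events. For them, neutrophil and platelet depth and duration are direct evidence of how well the combination is tolerated.

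Table 1 holds venetoclax at 400 mg and varies only quizartinib (20, 30 or 60 mg). Because the RP2D may be set below the MTD, toxicity short of a DLT is relevant to the choice. If a higher quizartinib dose deepened or prolonged cytopenia in responders, tables built from the CRF would not show it. Section 5.2.3 regards neutropenia as likely due to venetoclax, and CRF data could not examine that either.

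**Working it through.** The plan gives no figure for cytopenia, so there is none to reproduce. The check sets the sections side by side and then sizes the gap.

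**1. Is there another route for the values?**

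| Route | What it captures | Grade, nadir and duration of laboratory cytopenia? |
|---|---|---|
| 10.3 | Chemistry extremes per course | No; hematologic values barred |
| 10.2 | Adverse events, which include febrile neutropenia, infection, bleeding | Not stated for laboratory cytopenia; conflicts with or is limited by 10.3; Appendix G not available |
| 10.4 | SAEs, including blood dyscrasias | Serious cases only |
| 3.4 | Prolonged-myelosuppression DLT | Extreme cases only |
| 8.1 to 8.3 | CR, CRp and CRi, separated by neutrophil and platelet recovery | Recovery status at response; no grade or duration |
| 7.2.3 | Counts in the medical record | Source data exist, but no section has them tabulated |

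**2. Does the DLT route help at the dose decision?** Section 3.4 sets hematologic DLT at Day 42 or later with a hypocellular marrow, or at 8 weeks (8 × 7 = 56 days) with a normocellular one. Section 3.1 sets the DLT period at 28 days, section 11.3 ties the phase Ib Toxicity Summary to the first 28 days, and section 11.2 monitors DLT within one cycle.
- 42 − 28 = 14 days after the window closes
- 56 − 28 = 28 days after the window closes

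A hematologic DLT as defined cannot be seen inside the window. These passages must be reconciled.

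**3. Is the phase II toxicity stopping rule affected?** No; it counts DLTs only. With the stated Beta(0.6, 1.4) prior, the probability that toxicity exceeds 30% is 0.975 at 4/5, 0.962 at 6/10 and 0.960 at 8/15. With one DLT fewer it is 0.875, 0.880 and 0.893, all below 0.90. Table 5 therefore reproduces, and Table 6 reproduces to within 0.0001. Section 10.3 changes neither.

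**4. How many patients are involved?** Two assumptions are needed.
- *Patients with a cleared marrow*, using CRc as a proxy and the design's 25% and 50% (section 11.2): 0.25 × 20 = 5 and 0.50 × 20 = 10 in phase II.
- *Event rates*, borrowed from the venetoclax plus HMA study in section 2.5.5: neutrophil count decreased 31.1%, platelet count decreased 28.9%.

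| Cleared patients | Neutrophil event | Platelet event |
|---|---|---|
| 5 | 0.311 × 5 = 1.6 | 0.289 × 5 = 1.4 |
| 10 | 0.311 × 10 = 3.1 | 0.289 × 10 = 2.9 |

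The range is about 1.4 to 3.1 patients per event. In a phase Ib cohort of 6 at 50% CRc, 0.50 × 6 = 3 patients have a cleared marrow and 0.311 × 3 = 0.9 has the neutrophil event.

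**5. When do the data arise?** The scheduled disease-assessment marrow is at day 28 ± 7 of cycle 1 (section 7.2.6). Recording from the first leukemia-free marrow would mostly cover cycle 2 onward. It would inform phase II and later phase Ib cycles, and hardly the 28-day escalation decision.

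**The case against.** The strongest reply is that section 10.3 bars values, not events. Section 10.2 sends adverse events to the CRF with no hematologic exclusion, and the heading of 5.2.1 itself speaks of hematological adverse events. Febrile neutropenia, the most common event of grade 3 or above in the protocol's venetoclax plus HMA data (40.0%), remains reportable. Appendix G may already say how cytopenias are handled. The exclusion also fits the protocol's view that cytopenias are expected.

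Much of this stands, and it rules out several stronger readings:

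- *Myelosuppression is absent from the safety tables.* A reader might infer this from 10.3. The documents do not support it, because the clinical consequences, SAEs and hematologic DLTs have their own routes.
- *The RP2D is chosen without data on myelosuppression.* No section confines that review to CRF fields, and this is a single-institution trial with the counts in the medical record. What can be said is that no section requires them to be tabulated for it.
- *Myelosuppression is the main toxicity the two drugs share.* The quizartinib evidence in section 2.2 is from animals, section 2.2 also names QTc prolongation as its dose-limiting toxicity, and section 5.2.3 points to venetoclax for neutropenia.
- *About 6 of 20 phase II patients would go unrecorded for each event.* That applies the 31.1% and 28.9% to everyone. Those rates come from 45 treatment-naive patients aged 65 or older, on a different partner drug and regardless of marrow status.
- *Section 5.2.1 covers every patient with a clear marrow.* It is narrower. It plans no adjustment for myelosuppression in the first four cycles or with residual leukemia, and its thresholds then apply to responders with adequate pre-cycle counts.

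The reply does not supply a route for grade, nadir or duration. Response categories carry some information on incomplete recovery, but not these.

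**Conclusion.** The concern holds in a limited form. As far as the available text goes, laboratory neutropenia and thrombocytopenia in patients with a leukemia-free marrow cannot be summarized by grade, nadir or duration for each dose level from CRF data. That leaves a gap in the section 11.3 safety summary and in what the CRF can offer the RP2D review. It does not touch the primary endpoint or the stopping boundaries.

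The gap concerns roughly 5 to 10 of 20 phase II patients and about 1.4 to 3.1 patients per event. This rests on CRc standing in for a cleared marrow and on borrowed event rates that may not carry over to this population. The conclusion would weaken if Appendix G requires graded cytopenias on the CRF, but 10.3 would then contradict it and would still need correcting. The mismatch between the hematologic DLT definition and the 28-day window is separate and does not depend on these assumptions.

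**What to change.** 1. **Section 10.3.** From the first marrow with no evidence of leukemia, record per cycle the ANC and platelet nadirs, the days with ANC below 0.5 and the days with platelets below 20 × 10^9/L (thresholds already in 5.2.1), and the recovery date. Keep the exemption while leukemia is present. State whether the DLT exception covers hematologic values.
2. **Section 11.3.** Add a descriptive table or listing of these items by assigned quizartinib dose level. Do not plan a Kaplan-Meier comparison between cohorts of 6; with about 3 cleared patients per cohort at best under the design rates, it would not be informative.
3. **Consistency.** Align 10.2, 10.3 and Appendix G on whether laboratory cytopenias are adverse events for the CRF.
4. **DLT timing.** Reconcile the Day 42 and 8-week hematologic DLT definition in 3.4 with the 28-day window in 3.1, the one-cycle monitoring in 11.2 and the 28-day Toxicity Summary in 11.3.

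The cost is a few CRF fields per cycle in a minority to about half of patients, filled from counts already drawn, plus one table. No visit, test or treatment rule changes under items 1 to 3. Durations will be only as precise as the count schedule: at least twice weekly for three cycles, then weekly.

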10.5 Reporting to FDA

Serious adverse events will be forwarded to FDA by the IND Sponsor (Safety Project Manager IND Office) according to 21 CFR 312.32.

It is the responsibility of the PI, and the research team, to ensure serious adverse events are reported according to the Code of Federal Regulations, Good Clinical Practices, the protocol guidelines, the sponsor's guidelines, and Institutional Review Board policy.

10.6 Serious Adverse Event Reporting to Abbvie Inc and Daiichi-Sankyo.

All SAEs, whether related or unrelated to venetoclax and/or quizartinib, Quizartinib, pregnancies and reports of overdose regardless of suspected causality and expectedness will be reported immediately but not later than 24 hours of the PI becoming aware of the SAE to Abbvie's and Daiichi-Sankyo's SAE Management team who will ensure data is

captured in Abbvie's and Daiichi Sankyo Pharmacovigilance systems. The PI will forward completed SAE and pregnancy forms by fax to [contact] (Abbvie) and [contact] (Daiichi-Sankyo).

Address and phone number of person responsible for SAE management at Abbvie:
[contact]

The Alliance Pharmacovigilance Agreement executed on February 2018 between Daiichi Sankyo, Plexxikon and MDACC describes all Safety Information-related exchange obligations and will govern all ICSR case report exchanges between MDACC and Daiichi Sankyo. Any serious suspected unexpected adverse reaction (where SAE is not reported in the Investigator Brochure and is considered to be related to study drug) will be reported by the Investigator via email immediately to [contact].

Information not available at the time of the initial report (e.g., an end date for the adverse event or laboratory values received after the report) must be documented on a follow-up report. A final report to document resolution of the SAE is required. For any event of TLS, serious or non-serious, additional details maybe requested.

11.0 STATISTICAL CONSIDERATIONS

The primary objectives of the study are to evaluate safety and efficacy of venetoclax in combination with quizartinib in patients with FLT3-ITD mutated AML. The total accrual is 32 patients (Phase Ib: 12 patients and Phase II: 20 patients).

11.1 Phase Ib (Lead-in Phase)

The phase Ib portion is aimed at finding the MTD and RP2D of the two drugs in this combination. We plan to select a RP2D based on efficacy, toxicity, and PD data from the phase 1b dose-escalation. 3 patients at each dose level may not be sufficient to get a good estimate of efficacy and PD changes, and thus 6 patient dose escalation schema is proposed.

Patients will be enrolled in cohorts of 6 patients in the phase Ib portion of the study. The target dose is dose level +1, and the starting dose will be dose level 0. The first 6 patients on study will receive dose level 0.

The MTD is defined as the highest dose level with ≤ 1 out of 6 patients experience a DLT during the first 28 days of treatment. DLT is defined in section 3.4. The planned dosing algorithm is presented in section 3.3 and the dosing schema for the combination treatment is shown in Table 1. The RP2D will be selected at the end of the phase I portion based on reviewing the safety, efficacy, and PD data of quizartinib and venetoclax after discussion between the PI/Co-PI, the sponsor (MDACC IND office), and the supporting companies (Daiichi-Sankyo and Abbvie Inc). The Investigator is responsible for completing the cohort summary template prior to advancing subjects to the phase II part. Once RP2D has been established, any patients still on study at a dose lower than RP2D can be dose escalated up to RP2D in accordance with the dose-escalation guidelines in section 5.2.3.

The PK of quizartinib will be summarized statistically as n, geometric mean, %CV, median, minimum and maximum as Cmax and AUC0-24h of quizartinib and AC886 collected on Cycle 1 Day 7 (quizartinib alone) and Cycle 1 Day 8 (quizartinib + venetoclax) for the first 12 subjects. PK parameters will be dose normalized.

The PK of venetoclax will be summarized statistically as n, geometric mean, %CV, median, minimum and maximum for Cmax and AUC0-24h of venetoclax and M27 collected on Cycle 1 Day 8 (venetoclax + quizartinib) for the first 12 subjects. PK parameters will be dose normalized.

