Absorption: The time for quizartinib to reach maximum observed plasma concentration (Tmax) is approximately 4 hours in healthy volunteers and 2 hours in AML subjects. Food has minimal effect on the bioavailability of quizartinib: peak concentrations (Cmax) decreased by approximately 8% while area under the curve (AUC) values increased by approximately 5% to 8%. Food increased Tmax by approximately 2 hours. Quizartinib can be administered without any restriction on fed status. The proton pump inhibitor lansoprazole modestly decreased the absorption of quizartinib with Cmax decreased by 14% and AUC decreased by 5% to 6%. Quizartinib can be coadministered with gastric acid reducing agents (i.e. proton pump inhibitors, H2 blockers, and antacids).

At steady state in AML patients, the geometric mean (%CV) AUC0-24h for 30 mg QD and 60 mg QD were 3370 (72.5) and 8276 (95.7) ng·h/mL, respectively. The geometric mean (%CV) for Cmax at steady state for 30 mg QD and 60 mg QD were 186 (66.0) and 487 (80.8) ng/mL, respectively.

Distribution: Both quizartinib and its active metabolite, AC886, are highly plasma-protein bound with measured values >99% in all species tested. Both quizartinib and AC886 partition to red blood cells in a temperature-dependent manner. Blood samples must be processed at room temperature for accurate measurement of plasma quizartinib and AC886.

Metabolism: Reaction phenotyping using human liver microsomes and recombinant human CYP enzymes revealed that both quizartinib and AC886 were substrates of CYP3A, with little or no contribution of CYP2D6, CYP2B6, CYP2C8, CYP2C9, CYP2C19, or CYP1A2. The in vitro studies showed that quizartinib is metabolized to AC886 by CYP3A. The metabolite AC886 is, in turn, metabolized by CYP3A.

Steady state simulations of quizartinib coadministered with ketoconazole predicted that quizartinib Cmax and AUCltau increase by 86% and 96%, respectively, compared with quizartinib administered alone. Similarly, steady state simulations for quizartinib coadministered with fluconazole showed Cmax and AUCltau increases of only 20.1% and 20%, respectively. These results indicate that quizartinib should be dose reduced by approximately half when coadministered with a strong CYP3A inhibitor, but not a moderate or weak CYP3A inhibitor.

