3.3 Dosing algorithm

The goal of the lead-in phase Ib is to determine the MTD and RP2D. We will first treat 6 patients at dose level 0 in the phase Ib. If DLT occurs in $\geq 2/6$ patients, this dose level would exceed the MTD, and 6 patients will be treated at the next lower dose level (i.e. dose level -1). If DLT occurs in $< 2/6$ patients at dose level 0, the next cohort of 6 patients will be treated at the next higher dose level (i.e. dose level +1). The dose escalation or de-escalation (Table 1) will continue in cohorts of 6 until we reach the highest dose level at which $< 2/6$ patients experience a DLT in the first 28 days. The highest dose level at which 0-1/6 patients experience a DLT in the first 28 days of treatment will be the MTD. The RP2D will be selected from among the doses evaluated after reviewing the efficacy, safety, pharmacodynamics data. The RP2D selected may be lower than the MTD. The RP2D will be used to treat an additional 20 patients in the phase II expansion portion of the study.

If $\geq 2/6$ patients experience DLT at dose level -1, the study may be revised to consider additional lower dose levels.

Patients that are removed from study before day 28 for any reason other than toxicity and have not experienced DLT will be replaced.

*With up to 1 potential dose escalation level (+1) to be studied and up to 6 patients to be treated at a given dose, the target maximum number of patients projected to be enrolled in the phase Ib part of the trial will be 12.

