5.1 Schedule

All patients will be registered through CORe.

The Phase Ib dose escalation stage of the study will evaluate the safety, tolerability, PD and PK of venetoclax in combination with quizartinib, with the objectives of identifying the MTD and RP2D for each combination.

Quizartinib will be administered orally daily continuously starting on cycle 1 day 1. Patients will self-administer quizartinib tablets orally QD. If a dose is missed or vomited, the next dose should not be increased to account for missing a dose. The subject should take the next regular dose at the regularly scheduled time. Patients will receive one cycle of therapy every 28 days (+/- 7 days). Cycle 1 Day 1 of each cycle will be counted from the start of the quizartinib dosing. Quizartinib dose escalation criteria will be maintained as suggested in quizartinib Investigational Brochure (IB) as follows:

1. If the target dose for the given patient in the phase IB or phase II portion is quizartinib 30mg the patient will start the dosing on C1D1 at quizartinib 30mg per day
2. If the target dose for the given patient in the phase IB or phase II portion is quizartinib 60mg the patient will start the dosing on C1D1 at quizartinib 30mg per day and can increase to quizartinib 60mg per day on C1D12 only if QTcF on triplicate ECG is <450 msec on the Day 12 post-dose EKG

The initiation of venetoclax will be deferred for 7 days in cycle 1 to allow clinical and correlative evaluation of quizartinib single agent activity, and to debulk tumor burden thereby reducing the risk of tumor lysis syndrome (TLS). The intent is to initiate venetoclax on cycle 1 day 8. Blood samples will be collected at pre-dose, 2 (+/- 30 minutes), 4 (+/- 30 minutes), 6(+/- 30 minutes), 8 (+/- 30 minutes) and 24 (+/- 30 minutes) hours post-dose on cycle 1 day 14 to measure venetoclax, quizartinib and AC886 concentrations in patients enrolled in the dose-escalation period (n=12). The WBC count must be <10K prior to the initiation of venetoclax dosing. Note: Hydroxyurea can be used if needed during these initial 7 days to control WBC count, if needed.

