5.5.7 DRUG DRUG INTERACTION ASSESSMENT

Both quizartinib and venetoclax are CYP3A and Pgp substrates. Both quizartinib and venetoclax are Pgp inhibitors, and the latter also inhibits BCRP. Therefore, the potential for a two way drug drug interaction will be assessed in a substudy of the first 12 subjects enrolled in the Phase 1b. Specifically this substudy will assess the effect of venetoclax on quizartinib PK (i.e. Cmax and AUC0-24h) and the effect of quizartinib on venetoclax PK (i.e. Cmax and AUC0-24h) as summarized in section 5.1.

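### Section 11.1 plans only by-day summaries for the quizartinib interaction comparison: no within-patient ratio with an interval is planned, and the sampling days in 5.1 and 11.1 must be reconciled before one can be computed

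*Combined protocol and SAP*

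**What the plan says.** Section 5.5.7 gives the aim: "this substudy will assess the effect of venetoclax on quizartinib PK (i.e. Cmax and AUC0-24h) and the effect of quizartinib on venetoclax PK". It refers to section 5.1 for how this will be done.

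Section 11.1 names the statistics: "The PK of quizartinib will be summarized statistically as n, geometric mean, %CV, median, minimum and maximum". They apply to Cmax and AUC0-24h, for parent drug and metabolite alike, from samples "collected on Cycle 1 Day 7 (quizartinib alone) and Cycle 1 Day 8 (quizartinib + venetoclax) for the first 12 subjects", with dose normalization. No ratio, interval, test or no-effect range for PK appears there or elsewhere. The paired tests in 11.3 are for immunological and molecular changes.

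Section 5.1 schedules the PK draws at pre-dose and at set "hours post-dose on cycle 1 day 14 to measure venetoclax, quizartinib and AC886 concentrations in patients enrolled in the dose-escalation period (n=12"). By Day 14 both drugs are being given.

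Section 7.2.9 says that missed PK samples are not protocol deviations. Section 3.3 shows where the 12 comes from: "the target maximum number of patients projected to be enrolled in the phase Ib part of the trial will be 12", which is two dose levels of six.

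**The concern.** The aim is an effect: how much quizartinib exposure changes when venetoclax is added. As 11.1 describes the design, each patient serves as his or her own control, and the natural estimate is the within-patient ratio. The listed statistics describe each day separately. The %CV beside each geometric mean measures how much patients differ from one another. It does not show how precisely the change within patients is known. Because missed PK samples are tolerated, the two geometric means may also come from partly different patients.

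This substudy is the only planned evidence on the interaction. Section 2.2 names QTc prolongation as quizartinib's dose-limiting toxicity and describes it as dose dependent. A reader given two means with large %CVs and no interval cannot tell an absence of interaction from an absence of information.

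**Working it through.** **Stated figure.** n = 2 dose levels × 6 = 12. This reproduces the plan's number, but it is cohort arithmetic; no PK precision or power is stated.

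**Inputs.**
- Between-patient CV at steady state, section 2.2: "the geometric mean (%CV) AUC0-24h for 30 mg QD and 60 mg QD were 3370 (72.5) and 8276 (95.7) ng·h/mL". Under 5.1, patients with a 30 mg or a 60 mg target both take 30 mg up to Day 12, so 72.5% is the main case.
- Within-patient correlation ρ between the two log AUC values: not given. Assumed 0.3 to 0.8.
- Steady-state CVs are assumed to apply on Days 7 and 8.

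**Point estimate.** With 12 complete pairs, mean(log y) − mean(log x) = mean(log y − log x). The ratio of the two daily geometric means therefore equals the geometric mean of the within-patient ratios. The planned table gives the point estimate but not its standard error. With incomplete pairs the equality fails.

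**Precision.**
- SD of log AUC = √ln(1 + 0.725²) = 0.650.
- Days read as two independent groups: SE = 0.650 × √(2/12) = 0.265. With t(0.95; 22) = 1.717, the 90% factor is exp(1.717 × 0.265) = 1.58.
- Paired: SE = 0.650 × √(2(1 − ρ)/12), with t(0.95; 11) = 1.796.

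| ρ (assumed) | SE of log ratio | 90% CI factor, paired | 90% CI factor, as two groups |
|---|---|---|---|
| 0.3 | 0.222 | 1.49 | 1.58 |
| 0.5 | 0.188 | 1.40 | 1.58 |
| 0.7 | 0.145 | 1.30 | 1.58 |
| 0.8 | 0.119 | 1.24 | 1.58 |

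At CV 95.7% the SD of log AUC is √ln(1 + 0.957²) = 0.806. The same formulas give 1.76 as two groups, against 1.64 (ρ = 0.3) to 1.30 (ρ = 0.8) paired.

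**What the two-day ratio contains.** Section 2.2 gives a half-life of about 100 hours and an AUC accumulation ratio of 5.7, which implies 24 × ln 2 / −ln(1 − 1/5.7) = 86 hours. At a constant dose, AUC on day d is proportional to 1 − 2^(−24d/t½).
- Day 8 / Day 7: 0.736/0.688 = 1.07 (100 h) or 0.786/0.741 = 1.06 (86 h).
- Day 14 / Day 7: 0.903/0.688 = 1.31 (100 h) or 0.933/0.741 = 1.26 (86 h).

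So accumulation alone adds 6–7% from Day 7 to Day 8, and 26–31% from Day 7 to Day 14. Under section 5.5.4, Day 8 also carries only the first venetoclax ramp-up dose.

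**The case against.** Several objections have force.

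- **The paired design rests on 11.1 alone.** Section 5.5.7 points to 5.1, which schedules only Day 14, on both drugs. If 5.1 governs, there is no quizartinib-alone profile and nothing to pair. This stands, and it makes reconciling the days the first step.
- **The change is not lost.** A reader might infer that the plan never estimates it. The documents do not support that, because complete pairs give the point estimate from the two geometric means. Only its precision is missing.
- **No unpaired test is planned.** A reader might infer that the sponsor will compare the days as independent groups and miss a real interaction. Section 11.1 names no test, and no rule turns the table into a finding of no interaction. Nor would every effect be hidden. At ρ = 0.5, even a two-sided 5% unpaired t-test would detect a 1.96-fold change (the ketoconazole AUC figure in 2.2) with simulated power of about 74%.
- **A paired ratio is not a pure interaction estimate.** This stands: it includes accumulation and reflects an early ramp-up dose. A narrow interval labelled as the venetoclax effect would mislead.
- **Decision weight is limited.** PK is a phase Ib secondary objective, the RP2D rests on efficacy, safety and pharmacodynamics, and QTc is followed directly by ECG (7.2.8) and enters the DLT definition (3.4). That limits the seriousness, but 5.5.7 still promises an assessment of effect that 11.1 does not equip.

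**Conclusion.** The point holds in a limited form. Section 11.1 plans the two profiles in the same patients but no within-patient variability and no interval for the change, so the aim in 5.5.7 cannot be met with any stated precision. At CV 72.5% and 12 complete pairs, pairing narrows the 90% factor from a benchmark of 1.58 to between 1.49 and 1.24. The size of the gain depends on an assumed ρ of 0.3 to 0.8 and on steady-state CVs applied to early days. The point also depends on a quizartinib-alone profile being taken, on which 5.1 and 11.1 disagree. It is a worthwhile, inexpensive correction to a secondary objective and does not affect the phase II primary analysis.

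**What to change.** First reconcile the PK sampling days in 5.1 with those in 11.1; a paired analysis needs a quizartinib-alone profile. Then keep the descriptive table in 11.1 and add text such as:

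*For quizartinib and AC886, the within-patient ratio (combination day / alone day) of dose-normalized Cmax and AUC0-24h will be estimated in patients with both profiles, as a geometric mean ratio with a 90% confidence interval from a paired analysis of log-transformed values. Individual ratios will be listed. The ratio is the change between the two days: it includes quizartinib accumulation and reflects the venetoclax dose given on the combination day, so it is not a pure effect of venetoclax.*

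The cost is a short addition to 11.1 and minor analysis work. If the days in 11.1 stand, no patients or profiles are needed beyond those it already plans; if 5.1 stands, a quizartinib-alone profile would have to be added. Patients with only one profile drop out of the ratio but stay in the descriptive table. The change does not address the effect of quizartinib on venetoclax, for which 11.1 has no venetoclax-alone period.
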